## CONCLUSION

Both SI Kumbang and Bugar Lansia gymnastic exercises improved physical performance in older adults, as shown by significant gains in cardiorespiration endurance and physical activity in elderly. And there is no difference in physical performance aspects such as muscle strength, balance, and immunity aspects as Caspase-1 and IL-18 in the elderly.

These study results indicate that although both exercise modalities are effective in enhancing physical performance in elderly, SI Kumbang appears to provide superior benefits, particularly in improving cardiorespiration endurance and physical activity in elderly.

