A sample size of 33 people per group was determined. The study supervisor oversaw the use of a basic randomization program to carry out the random allocation. The Sequentially Numbered, Opaque, Sealed Envelope (SNOSE) technique was used to guarantee allocation concealment. Outcome assessors were subjected to single blinding; they were not told about group allocations and were not allowed to look for relevant information. The "SI Kumbang" and "Bugar Lansia" gymnastics exercise regimens were part of the intervention groups. For 12 weeks in a row, both therapies included three 30-minute sessions per week. Participants received adaption sessions to acquaint themselves with the workout regimens throughout the first week. The Borg Scale was utilized to track intensity.

The Six-Minute Walk Distance (6MWD) for cardiorespiratory endurance, and handgrip strength muscle measured using a handgrip JAMAR. The Physical Activity using Physical Activity Scale for the Elderly (PASE) questionnaire, the balance using Short Physical Performance Battery (SPPB) were among the outcome measures and the immunity aspect using inflammasome marker Caspase-1 and IL-18. The research team reviewed patient logbooks at the beginning of each week to track adverse effects such weariness, shortness of breath, pain, or dizziness. At RS Islam Jakarta Pondok Kopi, every suspected adverse event was swiftly assessed, and any required medical attention was given. Every adverse event was reported to the ethics committee of the institution.

Data analysis was performed using SPSS 29.0 tests with significance set at  $p<0.05$ . Descriptive summaries of the sample characteristics were provided. Prior to analysis, the normality of the data was checked. Dependent t-tests were used to compare pre intervention and post intervention score in the SI Kumbang and Bugar Lansia groups for normally distributed outcomes (6MWD, handgrip, SPPB, PASE, Caspase-1, IL-18); the Wilcoxon test was used to assess non-normal data. Independent t test or Mann-Whitney U test is used for compared the effectiveness of the two interventions ( $\Delta$  score). A p-value of less than 0.05 was deemed significant.

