Baseline characteristics of clinical outcomes of physical performance and immunity in elderly prior to intervention. Both groups are similar except for IL-18, which will be adjusted using ANCOVA analysis.

Table 2. Baseline Characteristics of Physical Performance and Immunity in Elderly before Intervention

| Variabel   | Si Kumbang
(n=33) | Bugar Lansia
(n=33) |
|---|------------------------------|--------------------------------|
| The Six-Minute Walk Test (6MWT) (meters), median (IR)              | 344,75 (293,75 – 376,5)      | 353 (311,25 – 375,75)          |
| Handgrip strength (kg), mean (SD)                                  | 16,11 (3,30)                 | 16 (3,39)                      |
| Skor The Short Physical Performance Battery (SPPB), median (RIK)   | 9 (9 – 11)                   | 9 (8,25 – 10,75)               |
| Skor The Physical Activity Scale for the Elderly (PASE), mean (SD) | 19,31 (2,73)                 | 20,67 (3,97)                   |
| CASPASE-1, mean (SD)   | 52251,52 (26750,02)          | 56129 (25767,23)               |
| IL-18, median (IR)   | 186,77 (136,37 – 295,03)     | 279,56 (190,67 – 438,45)       |

IR (interquartile range); SD (standard deviation)

The impact of the SI Kumbang group and Bugar Lansia group gymnastic exercise interventions on physical performance and immunity are displayed in Table 3. SI Kumbang group had significantly impact in cardiorespiration endurance (6MWD) ( $p=0.005$ ) and physical activity (PASE) ( $p = 0.001$ ). However, there was no significant impact on strength muscle (handgrip JAMAR) ( $p=0,136$ ), and balance (SPBB) ( $p=0,194$ ). Immunity in elderly showed, both group there were no significant in inflamasome Caspase-1 ( $p=0,055$ ) and IL-18 ( $p=0,327$ ). For IL-18, adjustment was performed using the ANCOVA test ( $p=0.255$ ).

Table 3. Impact Of “SI Kumbang” Exercise and “Bugar Lansia” on Physical Performance and In Elderly Analysis

| Variables                            | “SI Kumbang”
group (n=33) | “Bugar Lansia”
group (n=33) | p           | Adjusted |
|---|--------------------------------------|--|--------------------|-----------------|
|   | $\Delta$                             | $\Delta$                               |                    |                 |

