According to this study, elderly physical performance significantly improved because of both SI Kumbang and Bugar Lansia gymnastic exercise. Both groups showed substantial within-group improvements in the 6MWD, the same direction with a study by Casanova et al, which showed higher 6MWD values in the group that regularly performed aerobic exercise, with a 6MWD range of 380–782 meters. The impact of age on 6MWD became substantial at  $\geq 60$  years of age.

Significant variations in 6MWD can be explained by the gender, age, height, and weight of respondents. Degenerative diseases also increase with age, and even “apparently healthy” elderly people who are eager to participate in physical training sessions exhibit a wide range of health statuses.

Furthermore, a meta-analysis by Azimkhani et al. shows that endurance, aerobic, and combination exercise programs significantly improve cardiorespiratory endurance in older adults; the level of improvement depends on the intensity, duration, and adherence to the exercise program. Given the advanced age of the participants and the relatively short duration of the study intervention, these significant differences may be attributed to adequate exposure to training for improving cardiorespiratory endurance over 12 weeks, resulting in detectable physiological changes. Harber et al. emphasize that while improvement often requires sustained commitment to exercise therapy, accurate assessment of cardiorespiratory endurance, such as continuously increasing distance covered,

provides important insights into overall health and mortality risk.

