active and inactive elderly individuals. The significant difference in PASE scores between the SI Kumbang exercise group and the control group in this study likely reflects the interaction between environmental, social, and daily behavioral factors that influence increased physical activity among the elderly outside of exercise activities. The increase in the average PASE score in the SI Kumbang exercise group shows a promising trend that could lead to a significant increase in physical activity levels and better functional health outcomes.

The decrease in Caspase-1 levels in both groups indicates that the exercise intervention successfully reduced inflammatory activity in older adults associated with inflammasomes. These results are in line with a systematic review by Bautmans et al., which found that various types of exercise, especially those combining resistance and aerobic components, can reduce Caspase-1 and other proinflammatory cytokines such as IL-1 $\beta$ , IL-6, and IL-18, thereby altering the inflammatory profile of older adults. The downregulation of inflammasome signaling pathways is demonstrated by the reduction in Caspase-1, a crucial enzyme that activates cytokines from the IL-18 family. Although there were no differences in changes between the two exercise groups.

Following exercise intervention, IL-18 levels did not decrease because the analysis of the process pathway showed that caspase-1 activation requires various processes to produce a decrease in IL-18, that activated caspase-1 will cleave the same tetrapeptide site in pro-IL-18. The crystal structure of the caspase-1 and pro-IL-18 complex reveals a two-site (binary) substrate recognition mechanism, a catalytic pocket that binds the tetrapeptide, and a unique exosome that critically recognizes GSDMD10 and binds to a specific structure formed jointly by the propeptide sequence and the post-cleavage site in pro-IL-18. This binary recognition is also used by caspase-1 to process pro-IL-18; structural deviations around the exosite underlie its inability to target rationally designed pro-IL-18. The structure of pro-IL-18 displays an autoinhibitory interaction between the propeptide and the post-cleavage site region, preventing recognition by the IL-18R $\alpha$  receptor.

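### The Conclusion claims significant physical-activity gains for both programmes, but Table 3 implies p = 0.21 for Bugar Lansia, and two exercise arms cannot show that either programme works

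*Combined protocol and SAP*

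**What the plan says.** Methods sets out two kinds of test. Within arms, "Dependent t-tests were used to compare pre intervention and post intervention score in the SI Kumbang and Bugar Lansia groups" when the outcome is normally distributed, and "the Wilcoxon test was used to assess non-normal data". Between arms, the change scores are compared with an independent t-test or a Mann-Whitney U test. The threshold is 0.05.

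Table 3 (Result) prints each arm's change and one between-arm p-value per outcome. For PASE it gives 5.39 (4.38) for SI Kumbang, 1.16 (5.26) for Bugar Lansia and p = 0.001, marked as an independent t-test. No within-arm p-value is printed for any outcome.

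The Conclusion then says: "Both SI Kumbang and Bugar Lansia gymnastic exercises improved physical performance in older adults, as shown by significant gains in cardiorespiration endurance and physical activity". It adds that "both exercise modalities are effective in enhancing physical performance in elderly". The Discussion says that "elderly physical performance significantly improved because of both SI Kumbang and Bugar Lansia gymnastic exercise", and on the biomarker: "The decrease in Caspase-1 levels in both groups indicates that the exercise intervention successfully reduced inflammatory activity in older adults associated with inflammasomes".

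The Discussion treats the PASE result as a comparison between arms, referring to "The significant difference in PASE scores between the SI Kumbang exercise group and the control group in this study". The PASE statements in the Abstract and Result quote the same p = 0.001.

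**The concern.** Two claims go further than the evidence shown.

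First, the Conclusion names each programme and offers two outcomes as proof that it improved performance. A reader will take this as a significant PASE gain in each arm. A mean change of 1.16 against an SD of 5.26 in 33 people does not look significant. The printed p = 0.001 concerns the difference between arms, so it neither supports nor contradicts a gain within Bugar Lansia.

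Second, the trial has no unexercised arm. Randomisation supports a statement about which programme did better. It does not separate the effect of either programme from familiarity with the tests, regression to the mean, attention or time trends. Wording that credits the exercise itself therefore has no controlled comparison behind it.

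The Conclusion is what users of the report will cite. As it stands, it gives Bugar Lansia a result that the report's own table does not bear out, and gives both programmes an efficacy finding that the design cannot deliver.

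**Working it through.** **Inputs (Table 3).** PASE change, mean (SD): SI Kumbang 5.39 (4.38); Bugar Lansia 1.16 (5.26). Column headings give n = 33 per arm. Table 1 counts add to 36 per arm, so 36 is run as a sensitivity case. Tests are two-sided at 0.05; Methods does not state sidedness.

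**Step 1: reproduce the printed between-arm p-values.** If the brackets are SDs of change, equal-variance t-tests from the summary figures should return them.

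| Outcome | Printed p | n = 33 per arm | n = 36 per arm |
|---|---|---|---|
| PASE | 0.001 | 0.0007 | 0.0004 |
| Handgrip | 0.136 | 0.138 | 0.121 |
| Caspase-1 | 0.055 | 0.0549 | 0.045 |

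At n = 33 all three agree with print within rounding; at n = 36 Caspase-1 would fall below 0.05. Reading the brackets as SDs with 33 per arm fits.

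For PASE the contrast is 5.39 - 1.16 = 4.23. The pooled SD is sqrt((4.38² + 5.26²)/2) = 4.84 and the standard error 4.84 × sqrt(2/33) = 1.19, so t = 3.55 and the 95% CI is 1.85 to 6.61.

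**Step 2: apply the planned within-arm test.** Paired t = mean change / (SD / sqrt(n)).

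- Bugar Lansia: 5.26/sqrt(33) = 0.916; t = 1.16/0.916 = 1.27 on 32 df; p = 0.214; 95% CI = 1.16 ± 2.037 × 0.916 = -0.71 to 3.03.
- SI Kumbang: 4.38/sqrt(33) = 0.762; t = 5.39/0.762 = 7.07; p < 0.0001; 95% CI 3.84 to 6.94.

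**Step 3: can the Bugar Lansia result be moved below 0.05?**

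| Variation | p |
|---|---|
| Rounding of mean and SD, n = 33 | 0.212 to 0.217 |
| n = 36 | 0.194 |
| One-sided, n = 33 | 0.107 |

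At n = 33, p < 0.05 needs a mean of at least 2.037 × 5.26/sqrt(33) = 1.87, or an SD of at most 1.16 × sqrt(33)/2.037 = 3.27. With the printed mean and SD it needs at least 82 participants.

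**Step 4: the Wilcoxon alternative.** It cannot be computed without individual data, so its likely range was simulated: 4,000 samples of 33, each rescaled to mean 1.16 and SD 5.26. With a normal shape the median p is 0.23 (central 95% of values 0.10 to 0.44), and 0.2% of samples fall below 0.05. With a strongly left-skewed shape (a reversed exponential) the median p is 0.06, and about 41% fall below 0.05. A significant result thus needs clearly non-normal changes, which the t-test marker on PASE in Table 3 does not suggest.

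**Step 5: a pooled reading.** Combining the arms, the mean is (5.39 + 1.16)/2 = 3.275, SD 5.25, n = 66, t = 5.06, p < 0.0001, 95% CI 1.98 to 4.57. That is significant, but it is carried mainly by SI Kumbang.

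**Step 6: the rest of the sentence.** The Bugar Lansia 6MWD change has median +54 m and lower bracket +25 m. If that bracket is a quartile, about three quarters improved by at least 25 m; a conservative sign test with 24 of 33 positive gives p = 0.014. The 6MWD part holds as a change from baseline.

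**Step 7: the causal wording.** Caspase-1 shows why this is a separate point. Its within-arm changes imply t = -8.10 (SI Kumbang) and t = -4.71 (Bugar Lansia), both p < 0.0001. Even changes that clear are not shown to be effects of exercise, because no unexercised group was measured over the same period.

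**The case against.** Several points can fairly be made on the other side.

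- *No printed number is wrong.* True. The fault is a statement that the table does not support, and the p-value of 0.21 is inferred.
- *The sentence may be a misworded carry-over.* It names exactly the two outcomes with significant between-arm results, so a within-arm PASE test may never have been meant. That is plausible, but the sentence still tells the reader something different and still needs correcting.
- *A pooled gain may have been meant.* Methods plans no pooled test, and a pooled gain would not show that each named programme improved activity.
- *Bugar Lansia did improve on other measures.* As change from baseline this is right. By the same method, handgrip gives t = 5.21 (p < 0.0001) for Bugar Lansia and t = 2.43 (p = 0.021) for SI Kumbang. Median SPPB change is +2 and +3, and the 6MWD gain is accepted. Only the physical-activity example fails, in one arm, but it is one of the two the Conclusion chose.
- *The fault is local.* The Abstract's conclusion is comparative and makes no such claim for Bugar Lansia. Table 3's footnotes already name the between-arm tests. This limits the correction but does not remove the need for it.
- *The limit on efficacy claims applies to any trial of two active arms.* Yes. It matters here because the Discussion and Conclusion make those claims.
- *The 4.23 contrast has not itself been verified.* This stands as a caution. Baseline PASE was 19.31 against 20.67 (Table 2). If Tables 2 and 3 cover the same people, the post-treatment means are 24.70 and 21.83, a difference of 2.87. A baseline-adjusted estimate would lie between 2.87 and 4.23 for any slope from 0 to 1. The 33 versus 36 discrepancy is also unresolved. The figure is used here only because it is the planned change-score comparison.

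**Conclusion.** The concern holds. The claim of a significant physical-activity gain with Bugar Lansia is not supported by Table 3: the change is +1.16 (95% CI -0.71 to 3.03, p = 0.21), and the result is not borderline under rounding, either participant count or a one-sided test. This assumes that the brackets are SDs of change, which the reproduced between-arm p-values support, and that the paired t-test is the relevant within-arm test. Only a Wilcoxon test on clearly skewed individual data could plausibly differ.

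The statements that each programme is effective, caused the improvement or reduced inflammation also go beyond the design, whatever the within-arm p-values.

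The point is confined to that clause and the efficacy wording. The within-arm 6MWD gain is accepted, and the between-arm results in favour of SI Kumbang on PASE and 6MWD are untouched by it. It should be corrected because it changes a stated conclusion.

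**What to change.** 1. In the Conclusion, remove Bugar Lansia from the significant physical-activity claim and lead with the randomised contrast. For example: *PASE rose more with SI Kumbang than with Bugar Lansia (difference in change 4.23, 95% CI 1.85 to 6.61). Changes from baseline, descriptive only, were +5.39 (3.84 to 6.94) and +1.16 (-0.71 to 3.03).* The authors should replace these figures with values computed from the individual data.
2. Add one table with the within-arm results already planned in Methods, each with a 95% CI and labelled descriptive. Do not argue for a difference between programmes from one arm being significant and the other not.
3. In the Discussion and Conclusion, reword the statements that credit both programmes with the improvement, with lowering inflammatory activity, or with being effective. Describe each as a change from baseline without an unexercised comparison.
4. Where the Abstract and Result quote Table 3 p-values, say that they compare the two arms.

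The cost is wording and one descriptive table. No new data are needed, and no between-arm estimate or test changes. The stand-alone claim for Bugar Lansia becomes weaker.

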### Abstract

**Background:** The most common issue associated with aging is frailty, which has a significant impact on the physical performance and immunity of older adults. Exercise is the primary modality in medical rehabilitation. The Indonesian Strong and Balanced Healthy Exercise (SI Kumbang) gymnastic exercise is a newly designed exercise model developed by researchers, which is a type of low-impact aerobic exercise with moderate intensity. SI Kumbang exercises are performed three times a week for 30 minutes over a period of 12 weeks. The main basis of these exercises is foot movements that follow a rhythm, with the feet rotating in sequence in the four cardinal directions.

**Objective:** This study aimed to evaluate and compare the impact of SI Kumbang gymnastic exercises and Bugar Lansia gymnastic exercise programs on physical performance and immunity in elderly.

**Methods:** A randomized single-blind clinical trial involved 66 elderly participants aged 60–70 years, divided into SI Kumbang (n=33) and Bugar Lansia (n=33) groups. Each group exercised three times weekly for 12 weeks. Outcomes measured for physical performance were cardiorespiration endurance using Six-Minute Walk Distance (6MWD), strength muscle using handgrip JAMAR, balance using Short Physical Performance Battery (SPPB), physical activity using Physical Activity Scale for the Elderly (PASE). Outcomes measured for immunity were inflamasome using Caspase-1 and IL-18. Data were analyzed using SPSS 29.0 tests with significance set at  $p<0.05$ .

**Results:** Physical performance in elderly showed, SI Kumbang group had significantly impact in cardiorespiration endurance (6MWD) ( $p=0.005$ ) and physical activity (PASE) ( $p=0.001$ ). However, there was no significant impact on strength muscle (handgrip JAMAR), and balance (SPBB). Immunity in elderly

showed, both group there were no significant in inflamasome Caspase-1 ( $p=0,055$ ) and IL-18 ( $p=0,255$ ).

**Conclusion:** In conclusion, SI Kumbang gymnastic exercise group has more significant impact in terms of physical performance, particularly in enhancing cardiorespiration endurance and physical activity rather than Bugar Lansia gymnastic exercise group. And there is no difference in physical performance aspects such as muscle strength, balance, and immunity aspects as Caspase-1 and IL-18 in the elderly.

**Keywords:** elderly, physical performance, immunity, SI Kumbang exercise gymnastics.

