This study shows that there is no significant difference between the muscle strength of the SI Kumbang exercise group and the Bugar Lansia exercise group as measured by handgrip strength. Handgrip strength is a valid and simple measure of our total body muscle strength. Grgic et al. support this by finding that an aerobic exercise regimen can increase muscle strength depending on the intensity of the exercise, duration, and type of exercise movements and exercise load required for significant hypertrophy and muscle strength changes. In the SI Kumbang exercise, a 0.5 kg barbell weight was given to the hands, which did not significantly affect muscle strength improvement compared to the Bugar Lansia exercise, which did not use barbell weights in the hands. Therefore, further studies are needed on the weight of the barbell and the type of movements that involve the core muscles or large muscles more to optimize muscle strength improvement.

The results of the balance difference analysis with SPPB scores show that there is no significant difference between the two exercise groups. SPPB is valid, reliable, responsive, and measures physical function in the elderly population. A change of 0.5 points on the SPPB is considered small but significant, while a change of 1 point is considered substantial. Lu et al. highlight the significance of aerobic exercise in maintaining or improving physical function by emphasizing the predictive validity of the SPPB and physical performance measures in identifying older adults at higher risk of falling over time. Both exercise programs showed an improvement in balance after exercise, and the two programs showed similar results. Ansai et al. provided aerobic exercise to elderly individuals for 16 weeks and found no significant difference between exercise and balance and the risk of falling because the elderly require a combination of multi-component muscle movements.

Physical activity in this study was significant for the SI Kumbang exercise group. In the elderly population, PASE scores were closely related to their functional abilities and overall health status. Higher PASE scores are often associated with better mobility, increased muscle strength, and a reduced risk of chronic diseases. According to Ayvat et al., PASE is a sensitive tool for identifying physical inactivity in the elderly population and successfully distinguishes between

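### Non-significant tests are concluded as absence of a difference for strength, balance, Caspase-1 and IL-18, with no between-arm interval or equivalence margin

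*Combined protocol and SAP*

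**What the plan says.** The Methods plan tests for a difference only: "Independent t test or Mann-Whitney U test is used for compared the effectiveness of the two interventions", applied to change scores, with the rule "A p-value of less than 0.05 was deemed significant". The Results add one adjusted analysis: "For IL-18, adjustment was performed using the ANCOVA test". No equivalence or non-inferiority margin appears anywhere. On size, the Methods say only "A sample size of 33 people per group was determined", with no effect size, SD or power.

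Table 3 gives the change in each arm and a p-value. It gives no between-arm difference and no confidence interval, including for the IL-18 ANCOVA.

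The Results, and the parts of the Discussion on handgrip and SPPB, correctly call these comparisons not significant. The summarising sentences go further:

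- Conclusion: "And there is no difference in physical performance aspects such as muscle strength, balance, and immunity aspects as Caspase-1 and IL-18 in the elderly".
- Abstract, conclusion: "there is no difference in physical performance aspects such as muscle strength, balance, and immunity aspects as Caspase-1 and IL-18".
- Discussion, on Caspase-1: "Although there were no differences in changes between the two exercise groups".
- Discussion, on SPPB: "the two programs showed similar results".

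**The concern.** A difference test with p above 0.05 says that the data are compatible with no difference. It does not say that they are incompatible with a difference worth having. To conclude absence, one needs an interval narrow enough to lie inside a margin justified in advance. Here there is neither an interval nor a margin.

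Four of the six outcomes are affected, including both immunity markers. The same sentences set these outcomes against claimed superiority on 6MWD and PASE, so a reader will take the statement literally: the programmes differ on two outcomes and do not differ on four. For Caspase-1, with p=0.055, that reading is especially hard to defend.

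**Working it through.** **Inputs.** Table 3 reports mean (SD) change for only two of the four outcomes. The number per arm is 33 (Methods and the Table 3 heading). Differences are SI Kumbang minus Bugar Lansia.

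| Outcome | SI Kumbang | Bugar Lansia | Published p |
|---|---|---|---|
| Handgrip (kg) | 1.14 (2.69) | 2.06 (2.27) | 0.136 |
| Caspase-1 | −38,945.33 (27,628.63) | −24,957.94 (30,423.15) | 0.055 |

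**Formulas.** Pooled SD = √[(SD₁² + SD₂²)/2]; SE = pooled SD × √(2/n); t = difference/SE on 2n − 2 df; 95% CI = difference ± t(0.975) × SE. With n=33, df = 64 and t(0.975) is about 1.998. The Methods do not say whether tests are two-sided; the published p-values match two-sided tests.

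**Reproducing the published p-values.**

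- Caspase-1: difference = −38,945.33 + 24,957.94 = −13,987.39; pooled SD 29,059.5; SE = 29,059.5 × √(2/33) = 7,154.0; t = −1.955; p = 0.0549, against 0.055 published.
- Handgrip: difference = 1.14 − 2.06 = −0.92; pooled SD 2.489; SE = 0.613; t = −1.50; p = 0.138, against 0.136 published. Rounding of the four inputs alone allows 0.133 to 0.143.

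Welch's version gives the same p-values to three decimals. The calculation therefore matches the documents' own analysis.

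**The missing intervals.**

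- Caspase-1: −13,987 ± 14,292 gives **−28,279 to +304**. The mean baseline is (52,251.52 + 56,129)/2 = 54,190, so the estimate is 25.8% of baseline.
- Handgrip: −0.92 ± 1.22 gives **−2.14 to +0.30 kg**. The estimate is about 6% of the mean baseline of 16.06 kg.

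The documents give no threshold for an important difference on either outcome, so these percentages show scale only. The trial's own changes give another yardstick:

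- The Caspase-1 interval allows an extra fall of 28,279 with SI Kumbang, more than the whole Bugar Lansia fall of 24,958.
- The handgrip interval allows a shortfall of 2.14 kg with SI Kumbang, slightly more than the whole Bugar Lansia gain of 2.06 kg.

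An equivalence test at the 5% level uses the 90% interval. For Caspase-1 that is −25,927 to −2,047, which excludes zero.

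**What 33 per arm could detect.** Taking the observed SDs, the difference detectable with 80% power is pooled SD × √(2/33) × (1.96 + 0.84): about 1.72 kg for handgrip and about 20,042 for Caspase-1. Power for a difference of 0.5 SD is about 53%.

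**SPPB and IL-18.** Table 3 gives medians only (SPPB changes 3 and 2; IL-18 changes −0.03 and 10.41), and the ANCOVA is reported as a p-value only. No interval can be derived. The 1-point gap between the SPPB medians is not an effect estimate, so it shows neither similarity nor a difference.

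**Dependence on the number analysed.** Under headings of n=33, the Table 1 counts (SI Kumbang, Bugar Lansia) sum to 36, 36 for BMI class, gender and living history, and to 36, 35 for education. If the same means and SDs came from 36 per arm (df 70), Caspase-1 would have SE 6,849.4, t = −2.042, p = 0.045 and 95% CI −27,648 to −327; handgrip would have p = 0.121 and 95% CI −2.09 to +0.25. The published 0.055 and 0.136 fit 33, not 36.

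**The case against.** The fairest defence is that nothing is hidden. The tests, the threshold and every p-value are disclosed, the Results and much of the Discussion use the correct wording, and no equivalence aim is claimed. On this view the concluding sentences are loose shorthand. That is true of the body of the report, but it does not rescue the sentences themselves: the correct wording was available and was not carried into the Abstract conclusion or the Conclusion.

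A second objection is that the calculation with 36 per arm is hypothetical. The stated number is 33 throughout, the published p-values fit 33, and Table 1 might describe participants before dropout. This stands as far as it goes. The finding holds fully at 33, and the 36 case is only a reason to confirm the number before any interval is printed.

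A third is that the SPPB sentence may mean only that both programmes improved balance. That reading is possible, but the sentence still compares the programmes, with no interval behind it.

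Two practical cautions also stand. Intervals rebuilt from rounded summaries should be replaced by ones from the raw data. IL-18 is summarised by medians and its change tested by Mann-Whitney, so the ANCOVA residuals need checking before its adjusted difference is relied on.

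**Conclusion.** The concern holds. The concluding statement is stronger than the analysis can support for all four outcomes. For the two that can be checked, the data are inconclusive: Caspase-1 −13,987 (95% CI −28,279 to +304) and handgrip −0.92 kg (95% CI −2.14 to +0.30). The Caspase-1 estimate favours SI Kumbang, if a larger fall is better as the Discussion treats it; the handgrip estimate favours Bugar Lansia. Neither direction is established. For SPPB and IL-18 the size of the uncertainty is unknown until intervals are supplied.

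These figures assume 33 analysed per arm, two-sided tests, and the rounded means and SDs in Table 3. This should be corrected: it is an over-claim in the sentences most readers will carry away, and it can be put right from existing data.

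**What to change.** 1. Confirm the analysed number per arm and reconcile it with the Table 1 counts before printing any interval.
2. Add to Table 3 the between-arm difference with 95% CI for all six outcomes: t-based for handgrip, PASE and Caspase-1; Hodges-Lehmann for 6MWD and SPPB; and the ANCOVA-adjusted difference for IL-18, after checking its residuals. State the direction of subtraction.
3. In the Abstract and the Conclusion, replace the sentence with: *No statistically significant between-group difference was shown for handgrip (−0.92 kg, 95% CI −2.14 to 0.30; estimate favours Bugar Lansia), Caspase-1 (−13,987, 95% CI −28,279 to 304; estimate favours SI Kumbang), SPPB [estimate, CI] or IL-18 [adjusted estimate, CI]; no equivalence margin was set.* Take the final figures from the raw data.
4. In the Discussion, replace the Caspase-1 sentence with the corresponding part of that text, and replace the claim of similar SPPB results with the SPPB estimate and interval.

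The cost is small: one check of the number analysed, six intervals from the existing dataset, and rewording in four places. The conclusion becomes less definite.
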